3.3 Trial Population

The trial population will include male and female subjects, 18 to 65 years of age, inclusive, with a diagnosis of schizophrenia according to DSM-5 criteria. Subjects must have had at least 1 inpatient psychiatric hospitalization within 4 years (48 months) prior to screening. Subjects must have been prescribed oral antipsychotic treatment for at least 6 months or longer prior to screening. Approximately 493 subjects will be screened in order to enroll 320 subjects and complete 224 subjects.

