3.7.1.3.5 Month 6/Early Termination Visit

Month 6/ET (- 3/ + 2 days) will be an investigator visit for the subject. In addition, Month 6/ET visit evaluations are to be completed for any subject withdrawn from the trial at any time (for any reason other than full withdrawal of the consent). At the Month 6/ET visit, the following will be performed:

- Administer the suicidality assessment (C-SSRS Since Last Visit Version; [Section 3.7.3.5](#)).
- Perform vital signs assessment ([Section 3.7.3.3](#)).
- Monitor AEs, including device-related nonserious AEs ([Section 5](#)).
- Accountability of patches and Abilify MyCite product (aripiprazole tablet embedded with an IEM sensor) supplies performed for subjects remaining on Abilify MyCite treatment. Any treatment changes, including reason for the change, will be recorded in the eCRF.
- Review Abilify MyCite dashboard data every 2 weeks for subjects remaining on Abilify MyCite treatment.

Protocol 031-201-00301

- [REDACTED]
- [REDACTED]
- [REDACTED]
- [REDACTED]
- [REDACTED]
- [REDACTED]
- Healthcare utilization record evaluation ([Section 3.7.1.4](#)).
- [REDACTED]
- [REDACTED]
- [REDACTED]
- [REDACTED]

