7.3 Handling of Missing Data

For the primary variable, the analysis will be based on the proportion of days with good patch coverage during the trial and no imputation will be performed for missing data. For analysis of change from baseline (Day 1), last-observation-carried-forward (LOCF) and observed-cases (OC) methods will be used, as considered applicable. No imputation will be performed for other missing data, unless specified otherwise.

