5.1 Data/Data Sets Specifications

5.1.1 Data Sets Analyzed

The following analysis samples are defined for this study:

Enrolled Sample: comprises all subjects who sign an eICF for the trial and entered screening.

Safety Sample: comprises all subjects who receive at least one dose of study medication in the prospective phase.

Protocol 31-201-301 Interim Analysis Plan

Intent-to-Treat Sample: consists of all Enrolled Sample who met the study inclusion/exclusion criteria and who are intended to receive study medication in the prospective phase.

Modified Intent-to-Treat (mITT): dataset which will consist all ITT subjects entering the prospective phase who have taken at least 80% of the study medication for the specified analysis period, and had complete information on hospitalization during the specified analysis period; that is for the Month 1-3 mITT: the specified period will be Month 1-3 prospective/respective; for the Month 4-6 mITT and Month 1-6 mITT, the specified period will be Month 4-6 prospective/respective and Month 1-6 prospective/respective, respectively.

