7.1 Primary Efficacy Analysis Endpoint

The primary endpoint of this trial is the comparison of inpatient psychiatric hospitalization rates (proportion of subjects with ≥ 1 inpatient psychiatric hospitalization[s]) between the retrospective period (Months 1 to 3) while on oral standard-of-care antipsychotic treatment and the prospective period (Months 1 to 3) after the switch to Abilify MyCite. Primary analysis will use the mITT for Month 1 to 3.

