7.1.2 Technical Details

Inpatient psychiatric hospitalization is defined as closed (locked) ward or open ward inpatient psychiatric hospitalization, where the hospitalization is not primarily for psychosocial reasons.

The start date and end date of the retrospective period Months 1-3 are calculated in the following ways: start date = (Date signing informed consent - 28*6 Days) and end date = (Date of signing informed consent - 28*3-1 Days). The start date and end date of the prospective period Months are calculated as: start date = (Mycite start date) and end date = (Mycite start date + 28*3 - 1). Similarly, the start date and end date of the retrospective period Months 4-6 are calculated in the following ways: start date = (Date signing informed consent - 28*3 Days) and end date = (Date of signing informed consent -1 Days). The start date and end date of the prospective period Months are calculated as: start date = (Mycite start date + 28*3) and end date = (Mycite start date + 28*6 - 1).

Inpatient psychiatric hospitalization is deemed to occur during the retrospective (or prospective) Months 1-3 if:

- The hospitalization starts before the start date of retrospective (or prospective) Months 1-3 and continues into Months 1-3
- The hospitalization starts during the retrospective (or prospective) period.

Similarly, Inpatient psychiatric hospitalization is deemed to occur during the retrospective (or prospective) Months 4-6 if:

- The hospitalization starts before the start date of retrospective (or prospective) Months 4-6 and continues into Months 4-6
- The hospitalization starts during the retrospective (or prospective) period

All the above hospitalization in Months 1-3 and Months 4-6 will be counted in the Month 1-6 period.

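### The primary analysis set has no rule to keep a subject whose prospective admission is already documented but whose hospitalization record stops before Day 84

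*SAP*

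**What the plan says.** SAP 7.1 states: "Primary analysis will use the mITT for Month 1 to 3". SAP 5.1.1 puts two conditions on that set. Members are those "who have taken at least 80% of the study medication for the specified analysis period" and who "had complete information on hospitalization during the specified analysis period". Interim Analysis Plan 2.2.1 repeats both, so the same set drives the two interim decisions.

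SAP 7.1.2 gives the prospective period the "end date = (Mycite start date + 28*3 - 1", which is Day 84. It counts an admission as soon as it starts inside the period. The endpoint in SAP 7.1 is whether a subject had one or more inpatient psychiatric admissions.

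Protocol 7.3 says of the primary variable that "no imputation will be performed for missing data". The same sentence describes that variable in terms of patch coverage, which is not the hospitalization endpoint. Protocol 7.2 defines its own mITT by completion of the first 3 months of dosing.

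On early leavers, Protocol 3.7.1.3.5 says that "Month 6/ET visit evaluations are to be completed for any subject withdrawn from the trial at any time", except after full withdrawal of consent. On expected losses, Protocol 3.3 says: "Approximately 493 subjects will be screened in order to enroll 320 subjects and complete 224 subjects".

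**The concern.** Once a prospective admission is recorded, the subject's value is yes and no later missing day can change it. A completeness requirement that runs to the end of the window, with no exception for that case, can discard a primary outcome that is already known. An example is a subject who takes every dose to Day 70 (70/84 = 83%, so the medication condition is met), is admitted in that time, and then cannot be traced.

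The loss falls almost entirely on one side. Six months of psychiatric history must be available at entry (Protocol 3.1), so retrospective data are close to complete by design. Incomplete follow-up arises in the prospective period. Protocol 3.8.3.1 lists adverse events and the need for a disallowed treatment among the reasons for stopping, so a link between admission and leaving is plausible.

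If that link exists, the subjects removed carry more prospective admissions than those kept. The prospective rate is then too low, and the final test, the efficacy and futility decisions and the conditional power used for sample-size re-estimation all lean towards MyCite.

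**Working it through.** **Inputs.** Retrospective rate 15.5%, prospective 7%, difference 8.5 points; discordant cells 13.5% (yes/no) and 5% (no/yes), leaving 2% yes/yes (SAP 4). Final two-sided alpha 0.04528 (SAP 4). Enrolled 320, completing 224, so 96 leavers or 30% (Protocol 3.3). The leavers' admission rate q and the timing of exit are not in the documents and are assumed below.

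**1. The plan's own figure.** n = [1.960·√0.185 + 0.842·√(0.185 − 0.085²)]² / 0.085² = 199, and the simpler form (1.960 + 0.842)²·0.185/0.085² = 201. The stated 200 reproduces. Enrolment also does: 224/0.70 = 320.

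**2. Who is removed by this clause alone.** The medication condition needs 0.80 × 84 = 67.2 days, so anyone who leaves before about Day 68 already fails it. The completeness clause adds those who leave on Days 68-83. With uniform exit that is 96 × 16/84 = 18.3, about 18 subjects.

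**3. Effect on the estimate.** Take 7% in the 224 completers and a 15.5% retrospective rate in leavers as in completers. Rate with the late leavers included = (224 × 0.07 + 18q)/242; bias as a share of the effect = (rate − 0.07)/0.085.

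| q | Rate | Share of effect |
|---|---|---|
| 7% | 7.00% | 0% |
| 15.5% | 18.47/242 = 7.63% | 7% |
| 20% | 19.28/242 = 7.97% | 11% |

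**4. All 96 leavers, both mITT conditions together.** Rate = (224 × 0.07 + 96q)/320. At q = 15.5% it is 9.55% and the bias is 30% of the effect. At q = 20% it is 10.9% and 46%.

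**5. False favourable result with no true effect.** Set both periods at 15.5% in the 242, with 4.5% admitted in both and 11% in each discordant cell. Remove the 18 late leavers whole, so that n = 224. The prospective rate left is (0.155 × 242 − 18q)/224. The retrospective rate is held at 15.5% and the yes/yes cell is scaled with the prospective rate. With b and c the yes/no and no/yes cells, ψ = b + c, d = b − c and z = 2.002, the probability is Φ{[d√224 − z√ψ]/√(ψ − d²)}.

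- q = 15.5%: d = 0, giving 2.3%.
- q = 20%: prospective (37.51 − 3.60)/224 = 15.14%, b = 0.1110, c = 0.1074, ψ = 0.2185, d = 0.0036. Φ(−0.882/0.467) = 3.0%.
- q = 31%: prospective (37.51 − 5.58)/224 = 14.25%, b = 0.1136, c = 0.1012, ψ = 0.2148, d = 0.0125. Φ(−0.741/0.463) = 5.5%.

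These are single-look figures.

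**6. Why restoring only the known admissions is not enough.** Suppose leaving is unrelated to admission, with a constant hazard giving 7% by Day 84 and uniform exit. The average of 1 − exp(−λt) over 0-84 days, with λ = −ln(0.93)/84, is 3.54%, so 96 × 0.0354 = 3.4 leavers have an admission on record. Adding only these gives (15.68 + 3.4)/(224 + 3.4) = 8.4%, when the true rate is 7%.

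**The case against.** **The term is undefined.** SAP 5.1.1 does not say what complete information means and does not mention Day 84. The sensitivity analysis in SAP 7.1.3 narrows the mITT to subjects in study for at least 75 days, which would remove almost nobody if membership already required study presence to Day 84. A lenient reading is therefore possible. That weakens any claim that such subjects are certain to be dropped. It does not supply a rule that keeps them.

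**Stopping MyCite is not losing data.** Protocol 3.8.3.1 wants early stoppers followed for the whole trial to track healthcare use, and 3.8.3.3 lists medical records as a follow-up route. This stands: a stopper whose hospitalizations are still followed satisfies the clause. The problem is confined to subjects whose hospitalization record ends.

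**An ITT table is planned.** CT-5.1.2 repeats the primary comparison on the ITT Sample. It is not primary, and no rule says how incomplete follow-up enters it. The SAP 7.1.3 sensitivity analysis is a subset of the mITT and cannot bring anyone back.

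**Stronger readings that the documents do not support.**

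- A reader might infer that the exclusion manufactures retrospective-only discordant pairs. It cannot: the whole subject goes, and the pair removed is no/yes or yes/yes.
- A reader might attach the 30% and 46% figures to this clause. They cover all 96 planned non-completers, most of whom already fail the 80%-medication condition.
- A reader might equate the share of admitted subjects lost with the error inflation. Deleting only the admitted subjects gives false favourable rates of 5%, 10% and 20% for losses of 10%, 20% and 30%, but the clause also drops leavers without an admission. If all 96 leave at the common 15.5% rate, 30% of admitted subjects are lost and the error stays at 2.3%. What matters is the excess of admissions among leavers.

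**Conclusion.** The gap is real and should be closed. As written, the plan can discard a known primary outcome from the final test and both interim looks, and nothing else in it clearly restores that outcome.

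The direction is conditional. The bias favours MyCite if admission makes leaving more likely. It is absent if the two are unrelated, so a flat statement that the clause lowers the MyCite rate goes too far.

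The clause's own share is modest: about 7% of the planned effect at a 15.5% leaver admission rate and 11% at 20%, with the null error moving from 2.3% to about 3.0% at a 20% rate and 5.5% at 31%. These figures rest on uniform exit, on all 96 losses falling within the 84 days, on leavers sharing the 15.5% retrospective rate, and on q counting every admission to Day 84, including any after the subject left. The stated sample size of 200 before interim looks is not in question.

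**What to change.** In SAP 5.1.1 and 7.1.1, and Interim Analysis Plan 2.2 and 2.2.1:

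1. Score any treated subject with an observed inpatient psychiatric admission in prospective Days 1-84 as hospitalized, and keep that subject whatever is missing later. Waive both the completeness and the 80%-medication conditions expressly; relaxing completeness alone would restore only the late leavers.
2. Handle early leavers without an admission in the same analysis. Use hospitalization records to Day 84 where follow-up continues. Otherwise multiply impute the unobserved remainder given retrospective status and reason for leaving.
3. Add a tipping-point analysis that raises the imputed admission rate until significance is lost.
4. Apply the same rule to table CT-5.1.2.

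Step 1 should not be adopted without step 2, because it would overstate the prospective rate on its own. Protocol 7.2 (completion of 3 months of dosing) and 7.3 (no imputation, and the misplaced patch-coverage wording) need to be reconciled with the new rule.

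The cost is SAP, interim-plan and protocol wording plus modest programming, with no additional subjects. The downside is that part of the primary analysis then rests on an imputation model, and the estimated reduction may be smaller.

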5.1.2 Definition of Baseline and Last Visit

The following definitions of baseline values are applicable to all efficacy analysis and safety analysis unless otherwise specified.

Baseline values are defined as the last available evaluations prior to or on the date of the first MyCite treatment.

Last visit is defined as the last scheduled visit with available data.

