3.7.1.2 Screening Visit

Eligible subjects will come to the trial site, on a day agreed upon by the subject (and his or her caregiver/support person, if applicable) and the investigator, to undergo screening assessments.

At the screening visit, the following will be performed:

- Retrospective hospitalization and intervention data will be collected only after trial eligibility is confirmed.
- Informed consent ([Section 3.4.1](#)).
 - The subject must provide documented informed consent before any other trial assessments or procedures are performed.
 - If the subject has a caregiver/support person, that caregiver/support person also must provide written informed consent.
- Eligibility Assessment ([Section 3.4](#)).
 - All protocol inclusion and exclusion criteria will be reviewed by the investigator; only subjects who meet all of the inclusion criteria and none of exclusion criteria may be considered for further participation in the trial.
- Obtain demographic information and psychiatric history.
- Obtain urine sample for pregnancy test (women of childbearing potential [[WOCBP](#)]; [Section 3.7.3.2](#)).
- Confirm diagnosis of schizophrenia by DSM-5.
- Administer the suicidality assessment (C-SSRS baseline version; [Section 3.7.3.5](#)).
- Perform electrocardiogram (ECG) collection ([Section 3.7.3.4](#)).
- Perform vital signs assessment ([Section 3.7.3.3](#)).
- Monitor AEs, including device-related nonserious AEs ([Section 5](#)).
- Discontinue prohibited medications ([Section 4](#)).

Protocol 031-201-00301

- Smartphone verification: Each subject will be asked to confirm the availability of a suitable smartphone for the trial, in addition to confirming a wireless local area networking (wireless fidelity [Wi-Fi]) connectivity option is available to them. A subject with a smartphone that is not compatible with the Abilify MyCite app will be offered a loaner phone for the trial period.
- [REDACTED] (Section 3.7.2.1.2).

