3.7.1.3.1 Baseline (Day 1)

After completion of the screening visit assessments and procedures, the subject will return for the baseline visit.

At the baseline visit, the following will be performed:

- Obtain urine sample for pregnancy test (WOCBP; Section 3.7.3.2).
- Administer the suicidality assessment (C-SSRS Since Last Visit Version; Section 3.7.3.5).
- Perform vital signs assessment (Section 3.7.3.3).
- Monitor AEs, including device-related nonserious AEs (Section 5).
- Abilify MyCite system onboarding (Section 3.2.2.2).
- The following will be dispensed to the subject:
 - Abilify MyCite products (aripiprazole tablet embedded with an IEM sensor), supplies, and patches (prescribed dose is recorded) sufficient for 1 month (from baseline [Day 1] to Month 1).
 - Instructions on how to install the Abilify MyCite smartphone application.
 - User Guide for Abilify MyCite including introductory video and reference guides.
 - Contact information for the call center.

Protocol 031-201-00301

- The first dose of Abilify MyCite is to be taken at the baseline (Day 1) visit (in the clinic) during onboarding, unless they have already taken their daily dose. Subjects should not take their oral standard-of-care medication that morning before the baseline visit.
- Review subject and investigator dashboards with the subject.
- [REDACTED]
- [REDACTED]
- [REDACTED]
- [REDACTED]
- [REDACTED]
- [REDACTED]
- [REDACTED]

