3.7.3.5 Suicidality

Suicidality will be monitored throughout the trial using the C-SSRS.²² The C-SSRS was developed by a team of researchers at Columbia University to address the need for standardized classification of suicide reports to assess suicide risk. This scale consists of a baseline evaluation that assesses the lifetime experience of the subject with suicide events and suicidal ideation and a post-baseline evaluation that focuses on suicidality since the last assessment. The Baseline/Screening Version and the Since Last Visit version of the C-SSRS will be completed by trained trial site staff at the time points presented in the Schedule of Assessments [Table 3.7-1](#).

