7.6 Safety Analysis

In general, baseline measurements of safety variables are defined as the last measurements prior to the first dosing of Abilify MyCite for the prospective phase of the trial. All safety summaries will be descriptive in nature.

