7.4.2 Other Analyses

The dashboard data is collected every 2 weeks by physicians or caregivers. The summary statistics of dashboard access by month, at Month 3, and Month 6 will be provided. The features on decision/discussion making will be summarized by the following categories: pill ingestion data, Subject reported reason code for missed doses, missed dose alert, activity, rest, mood, and subject reported rest quality rating. The count and percentage of general medical/treatment decisions made as a result of MyCite data will be summarized as: no change to treatment, adherence counseling, provided patient education, recommendations on lifestyle changes, medication changes, referred to other service/specialist, other. Further the subgroup of medication changes (increase dose, decrease dose, added medication, stopped medication, alter medication) will also be summarized.

8 Safety Analyses

In general, safety variables will be summarized by incidence and listed for Safety Samples.

Safety variables to be analyzed include AEs, clinical laboratory tests, vital signs, ECGs, physical examination findings, weight, height, BMI, extrapyramidal symptoms (EPS), suicidality using the C-SSRS, investigator rating of injection site reaction, subject reported visual analogue scale (VAS) score of injection site pain.

In general, summary statistics of changes from baseline will be provided for safety variables based on all available data for each post-baseline visit and for the last visit as well. Baseline and last visit measurements of safety variables are defined as in [Section 5.1.2](#). Data from the unscheduled visits are included in the mean change from baseline calculation and in the incidence's calculation.

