8.1.6 Columbia Suicide Severity Rating Scales

Columbia Suicide Severity Rating Scales (C-SSRS) are assessed at baselines, and at Month 3 and Month 6. C-SSRS data at baseline are summarized for incidence of reporting:

- Suicidality
- Suicidal behavior (and its 4 types)
- Suicidal Ideation (and its 5 types)

Suicidality is defined as reporting at least one occurrence of any suicidal behavior or suicidal ideation. Suicidal behavior is defined as reporting any type of suicidal behaviors (actual attempt, interrupted attempt, aborted attempt and preparatory acts or behavior). Suicidal ideation is defined as reporting any type of suicidal ideation. In addition to the above three incidences, C-SSRS data collected from post-baseline are also summarized for incidence of reporting:

- Complete suicidality
- Emergence of suicidal ideation
- Emergence of serious suicidal ideation
- Worsening of suicidal ideation
- Emergence suicidal of behavior

Any completed suicide is considered as complete suicidality. Emergence of suicidal ideation is defined as having no suicidal ideation at baseline and reporting any type of ideation during treatment. Emergence of serious suicidal ideation is defined as having no suicidal ideation at baseline and reporting any type of suicidal ideation with ideation severity rating of 4 or 5 during treatment. Worsening of suicidal ideation is defined to occur when the most severe suicidal ideation rating during treatment is more severe than its rating at baseline. Emergence of suicidal behavior is defined as having no suicidal behavior at baseline and reporting any type of suicidal behavior during treatment.

Protocol 31-201-301 Interim Analysis Plan

The suicidal ideation intensity total score is the sum of intensity scores of 5 items (frequency, duration, controllability, deterrents and reasons for ideation). The score of each intensity item ranges from 0 (none) to 5 (worst) which leads to the range of the total score from 0 to 25. A missing score of any item for will result in a missing total score. If no suicidal ideation is reported, a score of 0 is given to the intensity scale.

The incidence of C-SSRS events and change from baseline in suicidal ideation intensity total scores are presented by nominal study visits as recorded in CRF without mapping to time window of the study week/month.

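### Under the SAP's general baseline rule the C-SSRS baseline is the Day 1 form, so a recurrence in a subject positive at screening but negative on Day 1 is labelled emergent, and can be labelled worsening

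*SAP*

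**What the plan says.** **Baseline rule.** SAP 5.1.2: "Baseline values are defined as the last available evaluations prior to or on the date of the first MyCite treatment". The definitions there are "applicable to all efficacy analysis and safety analysis unless otherwise specified". SAP 8 names suicidality by C-SSRS among the safety variables and adds: "Baseline and last visit measurements of safety variables are defined as in" section 5.1.2. Protocol 7.6 has a similar rule: "baseline measurements of safety variables are defined as the last measurements prior to the first dosing of Abilify MyCite".

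**Which form is given when.** At screening (Protocol 3.7.1.2): "Administer the suicidality assessment (C-SSRS baseline version". At Day 1 (Protocol 3.7.1.3.1): "Administer the suicidality assessment (C-SSRS Since Last Visit Version". Table 3.7-1 marks the Since Last Visit version at Day 1, Month 3 and Month 6/ET, and the Baseline/Screening version at screening only.

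**What each form covers.** Protocol 3.7.3.5 describes "a baseline evaluation that assesses the lifetime experience of the subject with suicide events and suicidal ideation" and a post-baseline evaluation limited to the time since the previous assessment.

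**How baseline is used.** SAP 8.1.6: "Emergence of suicidal ideation is defined as having no suicidal ideation at baseline and reporting any type of ideation during treatment". Emergence of serious ideation and of behaviour is built the same way. Worsening means that the worst on-treatment ideation rating exceeds the baseline rating. The section does not say which pre-dose form supplies the baseline.

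**The concern.** A baseline rule of this kind suits measurements such as vital signs, where the most recent pre-dose value is the best description of the subject at the start of treatment. The C-SSRS is different, because the two pre-dose forms ask about different stretches of time. Taking the later form replaces a lifetime history with a report on the screening interval. A subject whose screening form recorded ideation, and who was quiet between screening and Day 1, enters the analysis as having no ideation at baseline.

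At stake are the emergence and worsening rows of the suicidality tables (CT-8.13 and CT-8.14 in SAP Appendix 2), and the baseline incidence, which would leave out what the screening form recorded. The trial has no concurrent control, so the subject's own baseline is the only reference for calling a report treatment-emergent. The affected pattern is plausible: no exclusion criterion in Protocol 3.4.3 names suicidality, although the investigator or medical monitor may exclude a subject on judgement.

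**Working it through.** The documents give no figure on this point, so there is none to reproduce. The check traces the rule and then classifies every possible pattern.

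**Step 1. Which form is the baseline?** The pre-dose forms are the Baseline/Screening version (screening) and the Since Last Visit version (Day 1). SAP 5.1.2 takes the latest one available up to and including the date of first MyCite. That is the Day 1 form whenever it exists, and the screening form otherwise.

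**Step 2. What does it cover?** Screening runs from Day -45 to Day -1, so the Day 1 form looks back at most about 45 days.

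**Step 3. Classify the patterns.** Each assessment is positive (+) or negative (-) for the same kind of report (ideation throughout, or behaviour throughout). Under SAP 8.1.6, emergent means negative at baseline and positive on treatment.

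| Screening | Day 1 | On treatment | Emergent, baseline = Day 1 form | Emergent, baseline = worst of both forms |
|---|---|---|---|---|
| - | - | - | no | no |
| - | - | + | yes | yes |
| - | + | - | no | no |
| - | + | + | no | no |
| + | - | - | no | no |
| + | - | + | **yes** | **no** |
| + | + | - | no | no |
| + | + | + | no | no |

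One pattern of eight changes: positive at screening, negative on Day 1, positive on treatment. Where the Day 1 form is also positive, the two rules agree.

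**Step 4. Worsening.** Take ideation ratings of 4 at screening, 0 on Day 1 and 2 on treatment. Against Day 1, 2 > 0, so the subject has worsened. Against the worst pre-dose rating, 2 < 4, so the subject has not.

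**Step 5. Size, as an illustration only.** Let h be the share positive at screening, q the share of those negative on Day 1, and r the share of those with a report on treatment. The number relabelled is 320 × h × q × r, where 320 is the planned enrolment (Protocol 3.3). None of h, q or r is in the documents. The assumed ranges are h = 10% to 40%, q = 50% to 90% and r = 5% to 20%.

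- Low end: 320 × 0.10 × 0.50 × 0.05 = 0.8
- High end: 320 × 0.40 × 0.90 × 0.20 = 23.0

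A range from about 1 to 23 subjects shows only that the answer depends on rates the documents do not supply.

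**The case against.** The other side has several good points.

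- **Old events are not re-counted.** A reader might infer that past ideation or behaviour is itself tallied as emergent on MyCite. Protocol 3.7.3.5 rules this out: the later forms ask only about the time since the last assessment. A new on-treatment report is always needed, and the mislabelled case is a recurrence.
- **The screening form is not discarded.** It is the baseline if Day 1 is missing. SAP 8.1.6 also presents incidences by nominal visit, which could show screening as a visit of its own. Neither changes how emergence and worsening are defined when Day 1 is present.
- **The text may be merely ambiguous.** SAP 8.1.6 uses the plural of baseline, Protocol 3.7.3.5 calls the lifetime form the baseline evaluation, and SAP 5.1.2 allows exceptions. Both forms may have been intended, but no rule combines them, so the general rule governs.
- **Unequal look-back is not a misclassification rate.** The Month 3 form covers about 28 × 3 = 84 days against at most 45 for Day 1, a ratio of 84/45 = 1.9. A reader might take this as the size of the error. It compares windows and says nothing about how many subjects are relabelled.
- **Ideation and behaviour must be kept apart.** A subject with an attempt but no ideation at screening, then ideation on treatment, is emergent for ideation under either baseline.
- **A lifetime baseline has its own fault.** It would stop new on-treatment events from counting as emergent in anyone with a past history. The present rule errs towards over-counting, which is the cautious direction for safety. This stands, and it is why one baseline should not simply replace the other.

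**Conclusion.** The concern holds in a limited form. Followed as written, the SAP labels as emergent a recurrence in a subject who was positive at screening and negative on Day 1, and it can label as worsening an on-treatment rating below the one recorded at screening. This is the result of a stated rule, which 8.1.6 does not override.

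The conclusion rests on the Day 1 form being completed as scheduled and on 5.1.2 applying to the C-SSRS because nothing else is specified. The number of subjects cannot be derived; the range of about 1 to 23 of 320 rests wholly on assumed rates. Protocol 7.6 makes all safety summaries descriptive, and the primary and secondary endpoint analyses do not use this baseline. A reader might go further and say that the baseline rule is what prevents the table from separating a treatment signal from pre-existing suicidality. That limit comes mainly from the single-arm design, and a better baseline would reduce the mislabelling without removing it.

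**What to change.** In SAP 8.1.6, override 5.1.2 for the C-SSRS:

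1. Define baseline as the most severe ideation rating and any behaviour across all pre-dose C-SSRS assessments, screening and Day 1 together.
2. State which look-back is taken from the screening form, separately for ideation and for behaviour. The protocol describes only a lifetime look-back for that form, so the sponsor needs to say what was recorded and what will be used.
3. Report emergence and worsening twice: against this baseline and against the Day 1 form alone, that is, with and without lifetime history. The pair shows how many labels depend on the choice and guards against hiding true on-treatment emergence.

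Both forms are already collected, so no visit or data item is added. The cost is a short addition to the SAP text and one extra set of descriptive rows. Emergence counts under the combined baseline can only be equal to or lower than those under Day 1 alone, which is a further reason to show both.
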